#### 14.5 Electrocardiogram (ECG)

12-lead ECGs are collected throughout the study at every visit.

When ECG is collected multiple times, the average of all available values on the same day will be considered as one assessment for the summaries, except for Day 1 where averages will be by pre-dose and post-dose averages. The averages will be rounded to integer values.

Observed (average) of ECG variables (e.g., heart rate, PR interval, QRS interval, QT interval, QTcB and QTcF interval) and the changes from Baseline at each assessment time point will be summarized.

Observed (average) of QTcB and QTcF will also be categorized into the following categories (msec) and the number and percentage of subjects in each category will be summarized at each visit and for the overall post-Baseline maximum:

- Observed:  $\leq 450$ ,  $451 - \leq 480$ ,  $481 - \leq 500$ , and  $> 500$ ;  $> 450$ ;  $> 480$ .
- Change from Baseline:  $\leq 10$ ,  $11 - 30$ ,  $31 - 60$ , and  $> 60$ ;  $> 30$ .

For cardiologist's interpretations, the number and percentage of subjects with ECG results that are determined as normal or abnormal will be summarized at scheduled visits. The overall post-baseline worst interpretation will also be summarized (i.e. if a subject has one or more post-baseline ECG results that is/are considered as abnormal, this subject will be counted in the abnormal category). Cardiologist's interpretations will also be summarized in a shift table. The shifts from Baseline to overall post-Baseline worst interpretation will also be presented. For the by-visit shift summary, the denominator is the number of subjects with non-missing cardiologist's interpretation at Baseline and the given visit for the given treatment group of the antecedent DB study. For the summaries of shift from Baseline to the overall post-Baseline worst interpretation, the denominator is the number of subjects with non-missing Baseline and at least 1 post-Baseline cardiologist's interpretation for the given treatment group of the antecedent DB study.

Electrocardiogram variable average values will be considered PCI if they meet the criteria listed in Table 8. The number and percentage of subjects with post-baseline PCI values will be at each post-Baseline visit and for overall post-Baseline. For the by-visit summary, the numerator for the percentage is the number of subjects with a post-Baseline PCI ECG for the given parameter and visit, and the denominator is the number of subjects with non-missing values for the given parameter and visit. For the overall post-Baseline summary, the numerator for the percentage is the number of subjects with at least 1 post-Baseline PCI ECG for the given parameter, and the denominator is the number of subjects with at least 1 post-Baseline ECG value for the given parameter. A listing of overall and of all subjects with any PCI ECG values will be provided.

**Table 8 Criteria for Potentially Clinically Important ECG Values**

ECG Parameter	Unit	High PCI Criteria
QRS Interval	msec	≥120
PR Interval	msec	≥220
QTcB	msec	>500
QTcF	msec	>500
QTcB: change from baseline		>60 msec
QTcF: change from baseline		>60 msec

#### **14.6 Physical Examination**

Physical examinations are performed throughout the study at every visit in the clinic. Physical examination results (normal, abnormal, and not done) will be summarized in a frequency table by body system and visit. A listing of physical examination data will be listed.

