6.2 Safety Assessments

6.2.1 Physical Examination

A general physical examination will be conducted at Baseline and at all other designated visits. When a study visit takes place off-site, the physical examination will not be required. The physical exam procedures will include the following organ systems:

- Neurological
- Head, ears, eyes, nose, and throat
- Skin
- Cardiovascular
- Respiratory
- Abdomen
- Genitourinary (optional)
- Musculoskeletal

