**Table 1 Dosing Schedule Based on Weight at Baseline of the Present Study**

Weight	Dose	Total Daily Dose
12-20 kg	30 mL (6 g) BID	60 mL (12 g)
>20-35 kg	40 mL (8 g) BID	80 mL (16 g)
>35-50 kg	50 mL (10 g) BID	100 mL (20 g)
>50 kg	60 mL (12 g) BID	120 mL (24 g)

BID = twice daily

If the subject cannot tolerate administration of the full assigned dose the Investigator may instruct the caregiver to reduce study drug to a dose as low as 3 g (15 mL) BID. In addition, up to 4 doses (in total, consecutive or non-consecutive) may be held for this reason.

Study drug is administered twice a day, once in the morning and once in the afternoon or evening. There should be at least 8 hours between doses. The study drug may be given with or without food.

In addition to the study drug dispensed at the Baseline visit, additional investigational product will be shipped directly to the subject. Confirmation of delivery to the subject will be made by a visiting nurse. Study drug shipment, return, and accountability will be performed in accordance with the drug distribution plan.

Subjects will have assessments completed at Week 12, Week 52, Week 104, and Week 130. Assessments may be completed in the clinic or off-site, at the discretion of the Principal Investigator.

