### 5.1 General Data Reporting Conventions

Continuous variables will be summarized using the following descriptive statistics: number of subjects, mean, standard error (SE), standard deviation (SD), median, minimum, and maximum. For descriptive summaries of efficacy changes from baseline, the 95% confidence interval (CI), calculated as mean  $\pm$  1.96\*SE, will be presented. Unless specified otherwise, means, medians, and CIs will be presented to one more decimal place than the raw data, and the SDs and SEs will be presented to two more decimal places than the raw data. In general, the maximum number of decimal places is 4 and values will be truncated to 4 decimal places in situations where there are more than 4 decimal places. Wherever possible data will be decimal aligned.

Height, weight and BMI will be presented with a maximum of one decimal place.

Categorical variables will be summarized by the number of subjects and the percentage of subjects in each category; the number of subjects and the percentage of subjects with missing data will be summarized for demographic and baseline characteristics (if applicable). Categories with zero counts will not have zero percentages displayed. For demographic summaries, percentages will be calculated by using the total number of subjects in the given treatment group of the antecedent double-blind (DB) study (ACP-2566-003) as the denominator. Percentages will be presented with one decimal place.

Duration in months will be calculated as ([the number of days / 365.25] \*12).

Clinical laboratory assessment values that are collected with “<” or “>” signs will generally be analyzed as the numerical value without the sign in tables and figures. In listings, these data will be reported as collected with the sign.

For each continuous measure in safety and efficacy analyses, change from baseline results will be presented by treatment group of the antecedent DB study ACP-2566-003 and overall in two ways:

1. Main analysis: using the baseline of this study, as defined in [Section 5.5](#), to report the changes across the timepoints of this open-label Study ACP-2566-005.
2. Exploratory analysis: using the baseline from the antecedent study, ACP-2566-003, to report the changes across the timepoints of this open-label Study ACP-2566-005.

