## **14. SAFETY ANALYSES**

All safety analyses will be performed using the Safety Analysis Set. Safety summaries will be summarized using descriptive statistics by treatment group of the antecedent DB study and overall. For each continuous measure in clinical laboratory variables, vital signs, and electrocardiogram, change from baseline results will be presented in two ways as specified in Section 5.1.

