### **14.1 Primary Safety Endpoints**

The primary safety endpoints are:

- Treatment-emergent adverse events (TEAEs)
- Serious adverse events (SAEs)
- Withdrawals due to adverse events (AEs)
- Potentially clinically important changes in other safety assessments

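### The physical examination summary gives by-visit frequencies only, so it does not count subjects who move from normal at Baseline to abnormal later; a shift table like the one for the ECG interpretation would

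*SAP*

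**What the plan says.** SAP 14.6 plans two outputs for the physical examination. The first is the table: "Physical examination results (normal, abnormal, and not done) will be summarized in a frequency table by body system and visit". The second is a listing: "A listing of physical examination data will be listed". It plans no shift from Baseline and no worst post-Baseline result, and it states no denominator.

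Other parts of the plan bear on this:

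- **Endpoint concept.** SAP 14.1 includes among the primary safety endpoints "Potentially clinically important changes in other safety assessments". Protocol 6.2 lists the physical examination among the safety assessments.
- **Baseline comparison elsewhere.** SAP 14 states: "For each continuous measure in clinical laboratory variables, vital signs, and electrocardiogram, change from baseline results will be presented in two ways". A normal/abnormal result is not a continuous measure, so this rule does not reach the physical examination. SAP 14.3 adds shift tables for laboratory values. SAP 14.4 has change from Baseline and change-based criteria for vital signs.
- **Closest parallel.** In SAP 14.5 the cardiologist's ECG reading is also normal or abnormal. Those "interpretations will also be summarized in a shift table", by visit and to the worst post-Baseline reading, with denominators limited to subjects who have both readings.
- **Where the examination is done.** SAP 3.1 states: "Assessments may be completed in the clinic or off-site, at the discretion of the Principal Investigator". Protocol 6.2.1 states: "When a study visit takes place off-site, the physical examination will not be required".
- **Percentages.** SAP 5.1 gives the general rule: "Categorical variables will be summarized by the number of subjects and the percentage of subjects in each category". Not done is one of the named categories in 14.6.

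**The concern.** For a normal/abnormal safety result followed over time, the useful count is how many subjects were normal at the start and abnormal later. Separate frequencies at each visit give the totals but not the movements between them. This matters in Rett syndrome because abnormal findings at entry are to be expected. Protocol 1.1 describes scoliosis, breathing disruption, loss of hand use and late motor deterioration.

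A stable percentage abnormal could then be taken as no deterioration when it also fits new findings offset by resolved ones, or by subjects who were not examined or had left. The group examined also need not be the same at each visit. Examinations can drop out when visits are off-site, and later entrants are expected to have shorter follow-up.

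**Working it through.** **Planned number.** SAP 3.4 expects 85% of about 180 subjects to roll over: 180 × 0.85 = 153, which reproduces the plan's figure. It is used below only for scale. The documents give no rate of abnormal findings and no off-site share, so all such rates here are assumptions.

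**1. What the by-visit totals say about new abnormalities.** For one body system, let A₀ and A₁ be the numbers abnormal at Baseline and at a later visit, M₀ the number normal at Baseline and D₀ the number not done at Baseline. The number moving from normal to abnormal lies between

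- lower bound: max(0, A₁ − A₀ − D₀)
- upper bound: min(A₁, M₀)

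With all 153 examined:

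| A₀ | A₁ | M₀ | Lower | Upper |
|---|---|---|---|---|
| 60 | 60 | 93 | max(0, 0) = 0 | min(60, 93) = 60 |
| 46 | 46 | 107 | max(0, 0) = 0 | min(46, 107) = 46 |
| 46 | 56 | 107 | max(0, 10) = 10 | min(56, 107) = 56 |

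A net rise therefore guarantees some new abnormalities once it exceeds the number not done at Baseline, but the range stays wide. Equal totals guarantee nothing.

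**2. Whether the columns describe the same subjects.** Off-site visits can remove examinations at any visit. Follow-up also differs by design. SAP 3.1 anticipates about 29 months from first entry to commercial availability, when the study would end. The Week 130 analysis window in SAP Table 2 opens on Day 820, and 820 / 365.25 × 12 = 26.9 months. On that timeline, subjects who enter more than about 29 − 26.9 = 2.1 months after the first would not reach the window. The last column would then describe a different group from the Baseline column.

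**3. Effect of the unstated denominator.** If p is the proportion abnormal among those examined and q the proportion not done, the percentage abnormal with not done in the denominator is p × (1 − q). With p held at about 30% and N = 153:

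| Not done | Examined | Abnormal | % with not done counted | % of those examined |
|---|---|---|---|---|
| 0 (0%) | 153 | 46 | 30.1 | 30.1 |
| 31 (20%) | 122 | 37 | 24.2 | 30.3 |
| 61 (40%) | 92 | 28 | 18.3 | 30.4 |
| 92 (60%) | 61 | 18 | 11.8 | 29.5 |

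On the inclusive denominator, a true rise from 20% to 30% disappears if the not-done share goes from 10% to 40%: 0.20 × 0.90 = 0.18 and 0.30 × 0.60 = 0.18. If not done is excluded, the mechanical fall disappears (the small differences in the last column are rounding), but the percentage rests on fewer subjects, possibly different ones.

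**The case against.** Three stronger readings are tempting, and the documents do not support them.

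- **A reader might infer that new abnormalities cannot be seen at all.** They can. SAP Table 2 makes Baseline an analysis visit, so a Baseline column is likely and a large enough net rise would reveal some. The listing allows subject-level review. Protocol 7.1.1 counts an unfavourable and unintended sign as an adverse event, and it leaves out stable or intermittent chronic conditions only if they pre-date Baseline and do not worsen. SAP 14.2 tabulates treatment-emergent events. This route depends on investigator judgement, but it means the examination table need not be read alone.
- **A reader might infer that a primary endpoint is left unanalysed.** Protocol 9.5.2 specifies change summaries for ECG, vital signs and body weight, and laboratory parameters, and does not mention the physical examination. The SAP sets criteria for potentially clinically important values only for laboratory, vital-sign and ECG results. No passage promises such an analysis of the physical examination, so 14.6 contradicts nothing.
- **A reader might infer that the percentages necessarily move with the off-site share.** That holds only if not done is in the denominator. SAP 14.3 to 14.5 use non-missing denominators in many summaries, and 14.6 may be meant the same way. Even on the inclusive reading the table shows the not-done share. With an assumed 70% abnormal among those examined and 40% not done, it shows 42% abnormal (0.70 × 0.60) and 18% normal (0.30 × 0.60), so the reader recovers 42 / (42 + 18) = 70%.

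It is also fair to say that a shift table has limits. Subjects already abnormal in a body system stay in the abnormal-to-abnormal cell whether unchanged or worse. Pairing does not remove selection by visit location either. These limits stand, but none of these objections supplies the missing count of subjects who move from normal to abnormal.

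**Conclusion.** The point holds as a modest gap in the summary. The table in SAP 14.6 does not report the within-subject change from normal at Baseline to abnormal later, although SAP 14.5 reports exactly that for another normal/abnormal result. In the illustration with 60 of 153 abnormal at both visits, the totals fit anything from 0 to 60 newly abnormal subjects. That range assumes everyone is examined at both visits.

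The changing set of examined subjects makes column-by-column comparison unreliable whichever denominator is used. The fall in the percentage abnormal is conditional on an inclusive denominator and on assumed off-site shares. No data are lost and no stated analysis goes undelivered.

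**What to change.** In SAP 14.6, keep the frequency table and the listing, and add a shift table by body system:

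- **Shifts:** from Baseline to each post-Baseline visit, and from Baseline to the worst post-Baseline result, in the layout of SAP 14.5.
- **Denominator:** for each visit, subjects with that body system examined at Baseline and at that visit; for the worst result, subjects examined at Baseline and at least once afterwards. Setting this per body system matters because the genitourinary examination is optional under Protocol 6.2.1.
- **Not done:** a separate count, outside the percentages. State the denominator of the existing frequency table at the same time.

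A short note should say that the table does not show worsening within a body system already abnormal at Baseline, which remains covered by adverse event reporting.

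The cost is one further table from data already collected, using a layout already planned. It needs no protocol change and no extra procedures for subjects.

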#### **14.7 Other Safety Endpoints**

There are no other safety endpoints in this study.

## **15. INTERIM ANALYSIS**

No interim analysis is planned in this study; if a new drug application (NDA) submission happens before the completion of this study, an interim data cut will be scheduled for that purpose.

## **16. DATA MONITORING/REVIEW COMMITTEE**

Data from this study will be reviewed by the Data and Safety Monitoring Board (DSMB) for study ACP-2566-003.

## **17. COMPUTER METHODS**

Statistical analyses will be performed using Version 9.4 (or newer) of SAS® on a qualified and validated environment.

Validation and quality control of the tables, listings and figures containing the results of the statistical analyses will follow appropriate standard operating procedures.

## **18. CHANGES TO ANALYSES SPECIFIED IN PROTOCOL**

No changes are made to the analyses specified in the protocol.

## 20. APPENDICES

### 20.1 Schedule of Assessments

Period	Baseline	Open-label Treatment Period				Safety Follow-up
		Week 12	Week 52	Week 104	Week 130/EOT/ET	
Visit Frequency						EOT/ET +30 days
Visit Number	1	2	3	4	5	
Visit window (days)	N/A	±3	±7	±7	+7	+4
Type of Visit a	Clinic or Off-site					Telephone or Telemedicine
Informed consent	X b					
Inclusion/exclusion criteria	X					
Physical examination a	X	X	X	X	X	
Vital signs c	X	X	X	X	X	
Height	X	X	X	X	X	
Weight a	X a	X	X	X	X	
12-lead electrocardiogram (ECG) c	X d	X	X	X	X	
Clinical laboratory tests (hematology, chemistry)	X	X	X	X	X	
Urinalysis	X	X	X	X	X	
Serum pregnancy test e	X		X	X	X	
Rett Syndrome Behaviour Questionnaire (RSBQ)	X	X	X	X	X	
Clinical Global Impression–Improvement since Baseline of Study ACP-2566-004 (CGI-I) f	X	X				
Clinical Global Impression–Severity (CGI-S)	X	X	X	X	X	
Communication and Symbolic Behavior Scales-Developmental Profile™ Infant-Toddler (CSBS-DP-IT) Checklist	X		X	X	X	

Table abbreviations and footnotes are provided on next page.

## 20.1 Schedule of Assessments (Continued)

Period	Baseline	Open-label Treatment Period				Safety Follow-up
		Week 12	Week 52	Week 104	Week 130/EOT/ET	
Visit Frequency						EOT/ET +30 days
Visit Number	1	2	3	4	5	
Visit window (days)	N/A	±3	±7	±7	+7	+4
Type of Visit a	Clinic or Off-site					Telephone or Telemedicine
Overall Quality of Life Rating of the Impact of Childhood Neurologic Disability Scale (ICND)	X		X	X	X	
Rett Syndrome Clinician Rating of Hand Function (RTT-HF)	X	X	X	X	X	
Rett Syndrome Clinician Rating of Ambulation and Gross Motor Skills (RTT-AMB)	X	X	X	X	X	
Rett Syndrome Clinician Rating of Ability to Communicate Choices (RTT-COMC) a	X	X	X		X	
Rett Syndrome Clinician Rating of Verbal Communication (RTT-VCOM)	X	X	X		X	
Rett Syndrome Caregiver Burden Inventory (RTT-CBI)	X		X		X	
Dispensing and review of semi-structured caregiver diary, including seizure diary	X	X	X	X	X	
Concomitant medications	X	X	X	X	X	X
Assessment of adverse events	X	X	X	X	X	X
Optional caregiver interview g	X					
Study drug dispensed h	X					
Authorization of study drug dispensation h	X-----X					
Study drug return h	X-----X					
Study drug accountability h		X	X	X	X	

Abbreviations: EOT=end of treatment; ET=early termination

a Assessments may be completed in the clinic or off-site, at the discretion of the Principal Investigator. When a study visit takes place off-site, the physical examination will not be required. Weight should be measured whenever possible at off-site visits. Measurement of weight is necessary at Baseline in order to determine the starting dose. The RTT-COMC should be completed if possible, but it is not required.

- b Consent for the present study **must be** obtained prior to performance of the EOT procedures at the EOT visit in the antecedent study. Data from the EOT visit procedures of the antecedent study will be carried over as Baseline information in the present study, as applicable.
- c Vital signs will include body temperature, resting respiration rate, sitting systolic and diastolic blood pressure, and pulse rate. The sitting blood pressure will be measured after the subject has been sitting for  $\geq 3$  minutes.
- d ECGs will be completed in triplicate at Visit 1 (Baseline) before dosing. The ECG taken at the EOT visit in the antecedent study is the Baseline ECG of the present study. A single ECG will be completed at all other designated visits.
- e For subjects who have reached menarche and have not had surgical sterilization
- f The CGI-I assessments for each post-Baseline visit will be assessing improvement from Baseline of the antecedent Study ACP-2566-004.
- g Caregiver interviews will be conducted remotely via telephone at or before the final study visit (Week 130 [EOT/ET]). Participation in the caregiver interview is an optional component of the study requiring a separate informed consent.
- h Investigational product will be shipped directly to the subject. Confirmation of delivery to the subject will be made by a visiting nurse. Study drug shipment, return, and accountability will be performed in accordance with the drug distribution plan. In addition, study drug will be dispensed at the site during the Baseline visit when the visit is conducted in the clinic.

## 20.2 Summary of Version Changes

Version No:	Document History Description of Update	Author(s)	Version Date
1.0	Original version	[REDACTED]	18 February 2022
2.0	Amended version	[REDACTED]	26 June 2023
